### **2.3. Randomization**

Subjects are randomly assigned to one of the two treatment sequences, stratified by weight and dose group, via the interactive web response system (IWRS). In each dose group, the assignment to the two treatment sequences (ZNS:placebo or placebo:ZNS) is in a 1:1 ratio. The randomizations scheme is as follows.

**Figure 2: Planned Randomization Scheme**

\* Subjects who have not treated a migraine headache with blinded placebo during the 6-week run-in period will be considered screen failures.

## 2.4. Examination of Subject Subgroups

Subgroup analyses will be performed to examine the consistency of responses for subjects in the following subgroups:

- a. Sex: Males, females
- b. Age: 6-8 years old, 9-11 years old (at screening)
- c. Race: Caucasian, Asian, African American, Others
- d. Type of migraine by history: with aura, without aura, mixed
- e. BMI: dichotomize at median

## 2.5. Missing Data and Outliers

### 2.5.1. Missing Data

In general, missing data will not be imputed except for missing migraine headache diary data.

### **2.5.1.1. Imputation Method for Migraine Headache Diary Data**

1. If the predose diary is missing the pain intensity for a particular treatment period, then the subject is considered a non-responder for diary time points 0.5-hour, 1-hour, and 2-hour for that treatment period.
2. If all postdose pain intensity up to and including the 2-hour diary are missing for a particular treatment period, then the subject is considered a non-responder for those time points (0.5-hour, 1-hour, and 2-hour) for that treatment period.
3. If a subject receives rescue medication within 2 hours after dosing with study drug for a particular treatment period, the subject will be considered a non-responder for all the subsequent diary time points after rescue for that treatment period up to and including the 2-hour time point. Note: if subject diary includes records of rescue medication that started prior to the start of migraine, such medications will be ignored as incorrect diary entry. If rescue medications are recorded with missing start date/time, worse case will be assumed, i.e. that the rescue medication was taken at the same time as the migraine started.
4. If a subject naps or sleeps within 2 hours after dosing with study drug for a particular treatment period, the subject will be considered a non-responder for all diary time points up to and including the 2-hour diary time point for that treatment period.
5. No imputation will be done for the 24-hour time point (observed cases only).
6. Otherwise, missing diary data up to the 2-hour time point will be imputed by the last observation carried forward (LOCF).

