### **2.1.2. Full Analysis Set**

The full analysis set (FAS) includes all subjects who were randomized and administered at least one dose of post randomization study drug. The analysis of all efficacy variables will be performed using the FAS and will be analyzed separately for high dose and low dose groups.

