### 5.2.1.3. Multiple Imputation Analysis

If the dropout rate is > 20%, a multiple imputation analysis will be performed. The analysis will be as follows:

- a. Use logistic regression on Period 1 data to regress the response variable (0/1) on randomization weight group and treatment group.

$$\text{logit}(p) = \beta_0 + \beta_1 \text{trtp} + \beta_2 \text{wtgrp}$$

where  $p_j = \Pr(R_j = 1 | \text{trtp}, \text{wtgrp})$  and  $R_j$  is the response of subject  $j$ .

- b. For each observation with missing data in Period 2,
  - i. Calculate the predictive probability of response  $R_j = 1$   
$$p_j = \frac{\exp(\mu_j)}{1 + \exp(\mu_j)}, \text{ where } \mu_j = \hat{\beta}_0 + \hat{\beta}_1 \text{trtp} + \hat{\beta}_2 \text{wtgrp}.$$
  - ii. Draw a random uniform variable,  $u$ , between 0 and 1. If the value of  $u < p_j$ , impute  $R_j = 1$ ; otherwise, impute  $R_j = 0$ .
  - iii. Draw a random uniform variable,  $v$ , between 0 and 1. If  $v < 0.5$ , then impute baseline severity = 3; otherwise, impute baseline severity = 2.
- c. Analyze the data using the model as in primary analysis.
- d. Repeat the steps b-c above 25 times.
- e. Combine the results using Rubin's rule ([Rubin 1987](#)).

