## 8.6. Sensitivity Analysis with Multiple Imputations and Tipping-Point Analysis

**Step 1.** A dataset needs to be created with the following variables:

1. TRTP: planned treatment at the time of assessment
2. APERIOD: treatment period number (1 or 2)
3. TRTSEQP: planned sequence of treatments (ZNS-Placebo or Placebo-ZNS)
4. USUBJID: unique subject identifier
5. WEIGHTCAT: weight category (<50 kg or >=50 kg)
6. BASE: pre-dose headache severity
7. AVALC: response variable (Y = response achieved, N = not achieved).

The following rows need to be included:

1. Data for all subjects for the 2-hour timepoint in Period 1 with non-missing AVALC
2. Data for all subjects with missing AVALC for the 2-hour timepoint in Period 2. In these rows both BASE and AVALC will be missing.

**Step 2.** Use the dataset from Step 1 as input to perform logistic regression on Period 1 data and estimate the probability of response in Period 2:

```
proc logistic data=...;
  class trtp weightcat / param=ref;
  model avalc(event='Y') = trtp weightcat;
  output out=predicted p=pred_prob;
run;
```

In the output dataset PREDICTED the variable PRED\_PROB will indicate the predicted probability of response.

**Step 3.** To ensure results are repeatable and amenable to validation by double-programming, a seed value 2291601 will be used in all random number generation functions below. The value was chosen arbitrarily based on the protocol number.

For each value of penalization factor  $\Delta$  ranging from 0 to 1 in increments of 0.05 do the following.

For each subject with missing Period 2 result perform the following steps 25 times:

- Draw a random uniform variable,  $u$ , between 0 and 1 (i.e.  $u = \text{ranuni}(2291601)$ )
- If the subject receives ZNS in Period 2 and if the value of  $u < \text{PRED\_PROB} - \Delta$ , impute response (AVALC = 'Y'); otherwise, impute no response (AVALC = 'N'). This effectively penalizes the ZNS treatment by making it less likely to have a responder.
- If the subject receives Placebo in Period 2 and if the value of  $u < \text{PRED\_PROB}$ , impute response (AVALC = 'Y'); otherwise, impute no response (AVALC = 'N').
- Draw a random uniform variable,  $v$ , between 0 and 1 (i.e.  $v = \text{ranuni}(2291601)$ ).
- If  $v < 0.5$ , then impute pre-dose headache severity = 'SEVERE'; otherwise, impute pre-dose headache severity = 'MODERATE'.

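### Non-responder rules 1 and 2 are not limited to dosed periods, so an undosed Period 2 can be scored as non-response in SAP 2.5.1.1 but is missing in the imputation sections

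*SAP*

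**What the plan says.** - **Scoring rules (SAP 2.5.1.1).** Rule 1: "If the predose diary is missing the pain intensity for a particular treatment period, then the subject is considered a non-responder" at 0.5, 1 and 2 hours. Rule 2 gives the same result under this condition: "If all postdose pain intensity up to and including the 2-hour diary are missing for a particular treatment period". Rule 6 fills any other gap up to 2 hours by LOCF. Rules 3 and 4 carry an explicit dosing condition; rule 4, for example, begins "If a subject naps or sleeps within 2 hours after dosing with study drug for a particular treatment period". Rules 1 and 2 carry none.
- **Who is analysed.** The full analysis set (2.1.2) takes in randomized children who were "administered at least one dose of post randomization study drug". The primary analysis uses all high-dose children in that set (5.1), and its input dataset has one record for each subject and treatment period (8.1).
- **Imputation.** Section 5.2.1.3 imputes as follows: "For each observation with missing data in Period 2". Section 5.2.1.4 has the same target. Section 8.6, Step 1, selects Period 2 rows with no 2-hour response and says of them: "In these rows both BASE and AVALC will be missing". Step 3 of that section expects every child in the full analysis set to have a Period 2 result once the imputed rows are added.

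**The concern.** A child dosed only in Period 1 belongs to the full analysis set and has a Period 2 record with no predose and no postdose rating. On their wording, rules 1 and 2 score that record as a non-response to whichever treatment was assigned to Period 2. Section 8.6 requires the same record to have no response and no predose severity, yet a missing predose severity is exactly what triggers rule 1. The two sections cannot both be applied literally to this record.

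Two things are at stake. First, the multiple imputation and tipping-point analyses, planned for a dropout rate above 20%, would have an empty set of rows to impute. Second, outputs that use the response without the predose covariate would count an attack that was never treated as a failure, and only ever in Period 2. These are the McNemar test within each sequence and the percentages by sequence and period (5.2.1.1). The percentages are meant to show differential dropout and treatment-by-period interaction, so failures created in Period 2 alone would distort what they are there to reveal.

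**Working it through.** **1. Does any diary pattern leave the 2-hour response missing?** The predose, 0.5, 1 and 2-hour ratings can each be present or absent, giving 2 × 2 × 2 × 2 = 16 patterns. Applying rules 1, 2 and 6:

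| Pattern | Count | 2-hour response |
|---|---|---|
| Predose absent | 8 | Non-response (rule 1) |
| Predose present, all postdose absent | 1 | Non-response (rule 2) |
| Predose present, 2-hour absent, an earlier postdose rating present | 3 | LOCF (rule 6) |
| Predose and 2-hour present | 4 | Observed |

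The total is 16 and none is left missing. Rules 3 and 4 only turn values into non-response, so they add no missing values. If the rules apply to every treatment period, section 8.6 Step 1 finds no Period 2 rows.

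**2. Which outputs are exposed?** The primary GEE (5.1, 8.1) has predose severity as a covariate. No rule fills that covariate outside the imputation steps, so an undosed record would normally be dropped from this model and from the similar GEE models of 5.3. McNemar's test (8.4) and the percentages by sequence and period use the response alone and have no such filter.

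**3. Size of the effect on the by-sequence contrasts.** The plan gives no figure on this point. From the plan: 288 × 5/6 = 240 high-dose children, allocated 1:1, so 120 per sequence; target difference 0.11 (1.2). Assumed, because the SAP gives no rates: pain-free 30% on ZNS and 19% on placebo, no period effect, and a fraction L of each sequence undosed in Period 2, unrelated to response.

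With undosed periods scored as non-response:

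- ZNS then placebo: contrast = 30 − 19 × (1 − L)
- Placebo then ZNS: contrast = 30 × (1 − L) − 19

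| L | ZNS–placebo | Placebo–ZNS | Contrast if treated as missing |
|---|---|---|---|
| 10% | 12.9 | 8.0 | 11.0 |
| 20% | 14.8 | 5.0 | 11.0 |
| 30% | 16.7 | 2.0 | 11.0 |

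At L = 20% the average of the two is (14.8 + 5.0)/2 = 9.9 points. Keeping the 11-point difference and L = 20%: placebo 15% gives 26 − 12 = 14.0 and 20.8 − 15 = 5.8; placebo 30% gives 41 − 24 = 17.0 and 32.8 − 30 = 2.8. With no drug effect at all (19% on both), the contrasts would be 19 − 15.2 = +3.8 and 15.2 − 19 = −3.8, purely from the scoring.

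**4. McNemar power, placebo–ZNS sequence.** Assume zero within-child correlation. With discordant probabilities a and b, d = a − b and s = a + b, power = Φ[(d√n − 1.96√s)/√(s − d²)].

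- No loss, n = 120: a = 0.30 × 0.81 = 0.243, b = 0.19 × 0.70 = 0.133, d = 0.110, s = 0.376; power 0.50.
- 20% undosed, scored as non-response, n = 120: a = 0.8 × 0.243 = 0.1944, b = 0.19 × (1 − 0.24) = 0.1444, d = 0.050, s = 0.3388; power 0.15.
- 20% undosed, treated as missing, n = 96 pairs: d and s as with no loss; power 0.42.

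The fair comparison for the scoring rule is 0.15 against 0.42, since the lost pairs cost some power under either rule.

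**The case against.** The strongest reply is that the SAP already implies the restriction. The terms predose and postdose presuppose a dose. The windows in 2.9.2 are counted from dosing time, and without a dose there is no time zero. The statement in 8.6 that predose severity and response are both missing fits exactly if rules 1, 2 and 6 complete every dosed period and only undosed periods stay missing. On that reading, finding no missing pattern among dosed periods is expected. This is a good argument about intent. It does not replace a stated rule: the dosing condition is written into rules 3 and 4 and absent from rules 1 and 2, and the dataset specification asks for a record for every subject and period without exception.

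A reader might infer three stronger things that the SAP does not support.

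- **Bias, lost power or a raised type I error in the primary result.** Undosed records lack the predose covariate and would normally leave the primary GEE. The SAP plans no crossover GEE without that covariate, so figures from such a model would describe an analysis nobody is going to run.
- **Undosed children counted as drug failures.** That holds only in the placebo–ZNS sequence. In ZNS–placebo the undosed period becomes a placebo failure, which favours ZNS.
- **No remaining check on missing Period 2 data.** The completers analysis (2.1.3, 5.2.1.2) is planned regardless and excludes children not treated in both periods.

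It is also true that each by-sequence McNemar test is confounded with period in any case, and that it is a supportive analysis.

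**Conclusion.** The point stands as a conflict between a stated scoring rule and a stated analysis, with a probable but unwritten resolution. Taken literally, the rules leave the multiple imputation and tipping-point analyses with nothing to impute, and move the two by-sequence contrasts in opposite directions: 14.8 and 5.0 points against 11.0 each at 20% undosed. Those sizes rest on assumed response rates, equal and non-informative loss in the two sequences and no period effect; the conflict itself rests on none of these. The primary conclusion is largely protected. A correction is worth making because two programmers could follow the text in good faith and produce different supportive results.

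A related gap affects dosed periods. When study drug was taken but predose severity is missing, rule 1 scores a non-response, yet the primary GEE would drop the record for want of the covariate. As written, rule 1 therefore has no effect in the model it most needs to serve.

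**What to change.** 1. In 2.5.1.1, limit rules 1, 2 and 6 to treatment periods in which study drug was taken.
2. Add a sentence such as: *A treatment period in which no study drug was taken has a missing response; it is not set to non-response by this section, and it is what sections 5.2.1.3, 5.2.1.4 and 8.6 impute.* Individual imputation draws may still produce a non-response, which is consistent with this wording.
3. State that response percentages use dosed periods as the denominator and that McNemar's test uses children dosed in both periods.
4. State how a dosed period with missing predose severity, scored as non-response by rule 1, enters the primary GEE.

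The cost is a few sentences and no new data. Denominators become slightly smaller; in the illustration, McNemar's test would use 96 pairs per sequence instead of 120.

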Eligible placebo non-responders will be randomized to one of two treatment sequences within their respective body weight stratum determined immediately prior to randomization: ZNS followed by placebo or placebo followed by ZNS ([Table 1](#)). Subjects weighing less than 50 kg will be allocated randomly to receive ZNS 2.5 mg or 1 mg in a 5:1 fashion during the ZNS treatment. Subjects weighing at least 50 kg will be allocated randomly to receive ZNS 5 mg or 2.5 mg in a 5:1 fashion during the ZNS treatment ([Table 2](#)). Following randomization, subjects will have up to 6 weeks to treat a migraine attack of moderate or severe intensity. During each treatment period, subjects will treat a single moderate to severe migraine attack with study drug within approximately 20 minutes of the headache pain reaching moderate or severe intensity. Headaches occurring while the child is at school will not be treated with study drug. Headache pain intensity will be assessed by the subjects immediately prior to treatment with study drug and at 30 minutes, 1, 2, and 24 hours postdose using a subject diary containing the 4-point headache pain intensity scale. Associated migraine symptoms will also be assessed at these time points. Subjects who do not obtain satisfactory relief of migraine pain by 2 hours after taking study drug will be permitted to treat with their protocol-allowed pre-study acute migraine medication (eg,

nonsteroidal anti-inflammatory drugs [NSAIDs] or acetaminophen) at that time or at any time thereafter, if the headache does not resolve or if it recurs, with the exception that all triptans and ergot derivatives are prohibited for 24 hours following the dose of study treatment. After treating a migraine attack in the first treatment period, the subject will return to the study site to receive study drug for the second treatment period. Subjects will then have up to 6 weeks to treat a second migraine attack of moderate or severe intensity.

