### 2.9.2. Analysis Windows for Diary Data

Diary assessment may not occur exactly at the protocol-specified time points. For the purpose of analysis or Part 1, observations will be assigned to analysis windows.

The analysis windows for diary data in Part 1 are provided in [Table 4](#).

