**Table 4: Analysis Windows for Diary Data**

Nominal Time Point	Lower Limit from Dosing Time (Minutes)	Upper Limit from Dosing Time (Minutes)
headache first became severe or moderate	-60	0
30-minute	1	45
1-hour (60 minutes)	46	90
2-hour (120 minutes)	91	150
24-hour (1440 minutes)	151	2160

Diary records falling out of the windows above will not be assigned and will only be listed in listings.

If multiple, valid, nonmissing diary data exist in an analysis window, records will be chosen based on the following rules:

- In general, the predose value will be the last nonmissing value prior to the dosing time of study drug.
- For postdose assessments:

- The record closest to the nominal time for that visit will be selected.
- If there are 2 records that are equidistant from the nominal time, the nominal record (the one recorded on the correct diary time point) will be selected.
  - However, if there are 2 records that are equidistant, one is the actual time and one is the imputed time (due to missing data), the assessment with actual time will be selected.
- If there are 2 records with identical times, the one recorded on the correct diary time point will be used.

In the analysis of Part 2 the diary observations will be analyzed according to the nominal timepoint recorded in the diary.

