## **5. EFFICACY ANALYSES**

### **5.1. Primary Efficacy Endpoint in Part 1**

A patient diary is used to collect the patients' self-assessment of headache pain intensity. Pain intensity is rated on a 4-point scale: severe (3), moderate (2), mild (1), and none (0).

The primary efficacy endpoint is the proportion of subjects with pain-free status at the 2-hour time point for the high dose group during the double-blind phase of the study. Pain-free status is defined as a reduction in the headache pain intensity rating from moderate (2) or severe (3) pain at predose to none (0) at 2-hour post dose, without using rescue medication and without napping/sleeping prior to the 2-hour assessment.

For the primary efficacy endpoint analysis, all high-dose subjects in the FAS are included.

The primary endpoint will be analyzed using a generalized estimating equation (GEE). The model includes treatment, period, sequence, weight group (at randomization), and predose (immediately prior to study drug administration) headache pain intensity. The logit link function is used with an unstructured within subject covariance matrix. Odds ratio, p-value for the treatment effect and the corresponding 95% confidence interval will be presented.

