### **5.5. Changes From Protocol-Specified Efficacy Analyses**

If a subject naps or sleeps within 2 hours after dosing with study drug for a particular treatment period, the subject will be considered a non-responder for all diary time points up to and including the 2-hour diary time point for that treatment period.

The randomized population is replaced by the full analysis set. The completers population is further clarified as the double-blind completers analysis set.

The protocol inadvertently states that the McNemar's test was to be performed for Period 1 data. This SAP has corrected that the McNemar's test will be performed for each sequence.

Additional endpoints were added to the OLE endpoints to further elucidate the effect of ZNS:

- Proportion of subjects experiencing 2-hour pain free for  $\geq 20\%$ , 40%, 60%, and 80% of their treated moderate to severe migraine headaches.
- Proportion of treated moderate to severe migraine headaches that reduce to pain free at 2 hours:
  - o Descriptive summaries (mean, SD, median, min, max)
  - o Categorical summaries of  $\geq 20\%$ , 40%, 60%, and 80% of treated headaches

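### The rescue and nap rules stop at 120 minutes while the 2-hour rating may be taken up to 150 minutes, leaving late-rated attacks out of line with section 5.1 and the 2-hour headache response unprotected

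*SAP*

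**What the plan says.** Four parts of the SAP bear on this.

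- **Section 5.1** defines primary pain-free status as a fall from moderate or severe pain to none at 2 hours, "without using rescue medication and without napping/sleeping prior to the 2-hour assessment". The limit is tied to the assessment.
- **Section 2.5.1.1** gives the operational non-responder rules, and their limit is tied to the clock. Rule 3 applies "If a subject receives rescue medication within 2 hours after dosing with study drug for a particular treatment period" and fails the later time points up to and including 2 hours. Rule 4 applies "If a subject naps or sleeps within 2 hours after dosing with study drug for a particular treatment period" and fails every time point up to and including 2 hours. Section 5.5 repeats rule 4 among the changes from the protocol: "the subject will be considered a non-responder for all diary time points up to and including the 2-hour diary time point".
- **Section 2.9.2 and Table 4** expect off-schedule entries ("Diary assessment may not occur exactly at the protocol-specified time points") and give the window as "2-hour (120 minutes) 91 150", in minutes from dosing. Where several records fall in the window, the one closest to the nominal time is used. Neither the window nor the selection rule mentions rescue or sleep.
- **Section 1.1** says when rescue opens in the double-blind periods: "Subjects who do not obtain satisfactory relief of migraine pain by 2 hours after taking study drug will be permitted to treat", at that time or later.

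Section 5.3 defines the 2-hour headache response as a fall from moderate or severe to mild or none. It adds no condition on rescue or sleep. Recurrence and sustained response are built on the 2-hour results.

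**The concern.** The rules that turn diary entries into responder status use a different cut-off from the endpoint definition that they serve. The two agree when the rating is made by 120 minutes. They part when it is made later, which Table 4 allows for another 30 minutes. That is also when permitted rescue begins, so rescue taken as section 1.1 allows falls at or after the point where rule 3 stops.

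Two things are at stake:

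- **Primary endpoint.** A program built from section 2.5.1.1 alone would keep a late rating of none that section 5.1 disallows. The SAP does not state how the two sections combine.
- **2-hour headache response, and the recurrence and sustained-response endpoints that start from it.** Rules 3 and 4 are the only protection against counting relief that follows rescue or sleep, and they do not reach these attacks.

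**Working it through.** The SAP states no figure on this point to reproduce. The check compares time limits.

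**Inputs.** Let *r* be the time of rescue or nap and *a* the time of the record selected as the 2-hour rating, both in minutes from dosing. Table 4 gives 91 ≤ *a* ≤ 150. Rule 3 applies if *r* ≤ 120 and *r* < *a*. Section 5.1 excludes the attack if *r* < *a*.

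**Step 1: examples for rescue, each with a rating of none.**

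| Rescue *r* | Selected record *a* | Rule 3 | Section 5.1 |
|---|---|---|---|
| 110 | 130 | non-responder | not pain free |
| 120 | 130 | non-responder | not pain free |
| 121 | 120 | does not apply | rating stands |
| 125 | 145 | does not apply | not pain free |

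Only the last row shows a gap. Under the headache-response definition in section 5.3 that attack is a response, since nothing else excludes it.

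**Step 2: where the gap lies.** It needs 120 < *r* < *a* ≤ 150. In whole minutes, *r* runs from 121 to 149 and *a* from 122 to 150, giving 29 + 28 + … + 1 = 29 × 30 / 2 = 435 combinations. This maps the gap and is not a frequency. The upper 30 of the window's 60 minutes lie after the cut-off. With the rule proposed under the fix, none of the 435 remains.

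**Step 3: rule 4 before 120 minutes.** Rule 4 does not require the nap to precede the rating. A rating of none at 95 minutes followed by a nap at 110 is a failure under rule 4 but is not excluded by section 5.1. There the rule is stricter than the definition, which limits how the gap should be closed.

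**Step 4: selection.** Because the record closest to 120 minutes is used, a child who makes an on-time entry while still in pain is classified by that entry, and a later one is ignored. The gap needs a late selected record with no closer one in the window.

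**Step 5: scale, by assumption only.** Suppose 20–40% of attacks have the selected record at 121–150 minutes, 5–15% of those have rescue or sleep between 120 minutes and the record, and 20–40% of those are rated none. Then:

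- low end: 0.20 × 0.05 × 0.20 = 0.002, or 0.2% of attacks (0.002 × 240 = 0.5 attacks);
- high end: 0.40 × 0.15 × 0.40 = 0.024, or 2.4% (0.024 × 240 = 5.8 attacks).

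These are gross rates within one treatment. The treatment difference moves only by the difference between the two treatments' rates: zero if they are equal, and at most 2.4 − 0.2 = 2.2 percentage points either way within these ranges. For headache response the third share would be attacks rated mild or none, which cannot be smaller than the share rated none.

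**Step 6: what a net shift would mean.** Section 1.2 gives a difference of 0.11, SD 0.5, 240 subjects and two-sided 0.05. Taking the SD as that of the within-subject difference, power = Φ(difference × √240 / 0.5 − 1.96):

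- at 0.11: Φ(3.41 − 1.96) = 92.6%;
- at 0.10: 87.3%;
- at 0.09: 79.6%.

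These would apply to the primary endpoint only if section 5.1 were not enforced and placebo gained a net 1 or 2 points. If ZNS gained more, the difference would be overstated instead.

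**The case against.** A reader might infer that the SAP holds two conflicting definitions of the primary endpoint, and that a child rescued at 125 minutes and rated none at 145 would be counted as pain free. The documents do not support that. Rules 3 and 4 say when a subject is a non-responder. They do not say that nobody else is, and they declare no one a responder. Section 5.1 is the definition, and read together with the rules it fails this attack. A programmer who applies both sections gets the primary endpoint right.

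A reader might also infer a known bias, for instance against ZNS because rescue follows poor relief. The SAP gives no rates of late rating, rescue or sleep by treatment, so direction and size are open.

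It can further be said that the 2-hour assessment in section 5.1 means nominal minute 120, so that the texts agree. But Table 4 makes the analysed assessment an actual record, as late as 150 minutes. The nominal reading would also remove the protection that section 5.1 gives, and a rating made after rescue could then count as primary response.

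The objection that few attacks are affected may well be right. What stands after all this is a mismatch between the rules and section 5.1, and a real gap for the 2-hour headache response.

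**Conclusion.** The point holds in a limited form. Rules 3 and 4, and the nap rule in section 5.5, miss rescue or sleep that falls after 120 minutes but before a late record selected as the 2-hour rating. For the primary endpoint this is a lack of alignment with section 5.1, which still excludes the attack; misclassification is possible in programming but is not prescribed. For the 2-hour headache response and the endpoints built on it, the gap is substantive, because no other text excludes these attacks.

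Only attacks whose selected record lies at 122–150 minutes (in whole minutes), with no closer record in the window, can be affected. The range of 0.2% to 2.4% of attacks per treatment rests wholly on assumed shares and is gross. The net effect cannot be derived from the SAP. The alignment is worth making before unblinding because responder status should not depend on which section is programmed.

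**What to change.** Keep rules 3 and 4 as they are and add one rule to section 2.5.1.1:

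> If the record selected for the 2-hour window is later than 120 minutes after dosing, and rescue medication or a nap or sleep occurred after 120 minutes but before that record, the subject is a non-responder at the 2-hour time point only. Earlier time points are unchanged. If the time of the nap is not recorded, a nap reported at or before the 2-hour entry is taken to precede it.

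Apply it to 2-hour pain-free status and 2-hour headache response, and to recurrence and sustained response derived from them. Do not apply it to the rescue-use endpoints, which are properly clock-based. Bring section 5.5 into line.

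An addition is safer than replacing the 2-hour limit with the time of the rating. Replacement would turn some present failures into responders (rated none at 95 minutes, nap at 110). Under rule 4 it would also fail the 30-minute and 1-hour results because of a nap after 120 minutes.

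The cost is a short SAP edit and a change to the derivation program. Rescue start times and diary times are already used by the plan. The SAP does not show that nap times are captured, hence the default above. A few late-rated attacks become non-responders. The clinical rule on when rescue is permitted is not changed.
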